Furthermore, aRMMs are in place to mitigate important identified and potential risks associated with the use of filgotinib. These include a healthcare professional (HCP) Guide designed to increase awareness among HCPs by delivering specific information on contraindications, and warnings and precautions. Moreover, there is a patient alert card (PAC) to enhance awareness of risks and early signs and symptoms relating to specific adverse drug reactions and the best course of action to take.

On 10 February 2022, the Pharmacovigilance Risk Assessment Committee (PRAC) started a review of the safety of JAKi's for treatment of various chronic inflammatory disorders (including UC) under Article 20 of Regulation (EC) No 726/2004 (European Medicines Agency, 2022). This was triggered by the results of the 'Oral Surveillance Study' – an open-label, non-inferiority, post-authorization safety RCT involving patients with active rheumatoid arthritis aged  $\geq$  50 years and with at least one additional cardiovascular (CV) risk factor. The study suggested an increased risk of major adverse cardiovascular events (MACE) and malignancies in patients treated with the JAKi tofacitinib compared with tumor necrosis factor (TNF) $\alpha$  inhibitor treated patients (Ytterberg et al., 2022).

On 10 March 2023, with the EC's final decision on Article 20, the measures recommended by PRAC to minimize the risk of serious adverse events with JAKi's (including CV conditions, VTE, malignancies and serious infections) were endorsed. It was recommended that JAKi's should only be used in patients aged 65 years or above, those at increased risk of MACE, those who smoke or have done so for a long time in the past, and those at increased risk of malignancies "if no suitable treatment alternatives are available".

Based on the above PRAC recommendations and the approved key concepts in the summary of product characteristics (SmPC) (https://www.ema.europa.eu/en/documents/product-information/jyseleca-epar-product-information\_en.pdf), the marketing authorization holder (MAH) of filgotinib updated the existing HCP Guide and the PAC to reflect the changes in SmPC for filgotinib following the EC's final decision on Article 20.

Furthermore, a direct healthcare professional communication (DHPC) was issued to inform prescribers on the identified risks related to serious and opportunistic infections, and the potential risks of malignancies, VTE, and MACE.

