The safety information in the HCP Guide provides context and risk management advice for key safety aspects of the SmPC, namely (key safety aspects with updates in the HCP Guide after Article 20 are listed in *italics*):

- Serious and opportunistic infections
- Herpes zoster
- Potential risk of birth defects if filgotinib is taken during pregnancy

- Potential risk of VTE
- Potential risk of MACE
- Potential risk of malignancy
- Prescribing in elderly patients and in patients with risk factors for VTE, MACE, and malignancy

The SmPC specifies that the recommended dose for induction treatment in UC is 200 mg once daily. The recommended dose for maintenance treatment is 200 mg once daily. In patients aged 65 years or older or at higher risk of VTE, MACE and malignancy, the recommended dose is 200 mg once daily for the induction treatment which may be prolonged up to Week 22, and 100 mg once daily for maintenance treatment. In case of flare of the disease, the dose may be escalated to 200 mg once daily. For long term treatment, the lowest effective dose should be used (as per SmPC Section 4.2 'Posology and method of administration').

In patients with active tuberculosis (TB), active serious infections, or in women who are pregnant treatment with filgotinib is contraindicated (as per SmPC Section 4.3 'Contraindications').

Additional aspects as per updated SmPC Section 4.4 'Special warnings and precautions for use' are listed below:

*Use in patients 65 years of age and older*: Considering the increased risk of MACE, malignancies, serious infections, and all-cause mortality in patients 65 years of age and older, filgotinib should only be used in these patients if no suitable treatment alternatives are available.

*Infections*: As there is a higher incidence of infections in the elderly and in the diabetic populations in general, caution should be used when treating the elderly and patients with diabetes.

*Malignancy*: In patients 65 years of age and older, patients who are current or past long-time smokers, or with other malignancy risk factors (e.g. current malignancy or history of malignancy), filgotinib should only be used if no suitable treatment alternatives are available.

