*MACE* (i.e. fatal and nonfatal CVD events; CVD comprises coronary heart disease [angina, myocardial infarction], congestive heart failure, cerebrovascular disease and peripheral artery disease]): In patients 65 years of age and older, patients who are current or past long-time smokers, and patients with history of atherosclerotic CVD or other CV risk factors, filgotinib should only be used if no suitable treatment alternatives are available.

*VTE* (includes deep venous thrombosis) and pulmonary embolism [PE]): In patients with CV or malignancy risk factors filgotinib should only be used if no suitable treatment alternatives are available.

In patients with known VTE risk factors other than CV or malignancy risk factors, filgotinib should be used with caution. VTE risk factors other than CV or malignancy risk factors include previous VTE, patients undergoing major surgery, immobilization, use of combined hormonal

contraceptives or hormone replacement therapy, inherited coagulation disorder. Patients should be re-evaluated periodically during filgotinib treatment to assess for changes in VTE risk.

Patients with signs and symptoms of VTE should promptly be evaluated and filgotinib be discontinued in patients with suspected VTE, regardless of dose.

This longitudinal drug utilization study (DUS) is being conducted by the MAH as a Category 3 commitment to the EMA and to the Medicines and Healthcare products Regulatory Agency (MHRA) based on real-word secondary data derived from the same 3 IBD registries used for the filgotinib LTS PASS (GLPG0634-CL-413), namely the Estudio Nacional en Enfermedad Inflamatoria Intestinal sobre Determinantes Genéticos y Ambientales (ENEIDA) Register from Spain, the Initiative on Crohn and Colitis (ICC) Register from the Netherlands, and the Swedish National Quality Registry for Inflammatory Bowel Disease (SWIBREG).

This protocol follows the approach used in the already endorsed DUS for filgotinib in RA (GLPG0634-CL-408), thereby also taking into account prior comments from the PRAC Rapporteur.

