## 8.3.1. Patient Baseline Characteristics

Baseline variables are collected at the index date. These variables reflect the patient's demographics and status at the initiation of filgotinib treatment including relevant medical history at or prior to the index date. Baseline variables will include (as per availability by each registry):

- Age (at baseline)
- Sex
- Body mass index (BMI)
- Long-time smoking (for >10 years (Kristensen et al., 2023) (either current or past smoking)
- Date of UC diagnosis

- Severity of UC (for details, see Annex 3 Table 5)
- Renal impairment (for details, see Annex 3 Table 5)
- Hepatic impairment
- Type and number of previous UC treatments prior to filgotinib initiation
- Date of filgotinib initiation
- Initial filgotinib dose
- Diagnosis of active TB at index date
  - Date of diagnosis
- Active serious infection at index date
  - Date of diagnosis
- Current pregnancy (at index date)
  - Start of pregnancy
- Age  $\geq 65$  (at index date)
- History of atherosclerotic CVD (angina, coronary heart disease, myocardial infarction, congestive heart failure, stroke, peripheral arterial disease)
- Other CV risk factors (diabetes mellitus, hypertension, obesity/BMI  $\geq$  30 kg/m^2)
- Current malignancy
- History of malignancy
- Concomitant use of other immunosuppressants
- Diagnosis of viral hepatitis
  - Date of diagnosis
- Diagnosis of herpes zoster
  - Date of diagnosis
- Screening for viral hepatitis
  - Date of screening
- Laboratory measurements (measurement within ±1 month of filgotinib index date, or any time during follow-up)
  - absolute neutrophil count (ANC)
  - absolute lymphocyte count (ALC)
  - hemoglobin (Hb)
- Use of live-attenuated vaccines
- History of VTE
- Recent surgery (i.e. surgery within 1 month (Singh et al., 2023) prior to the index date or at any time during follow-up; see also Annex 3 Table 5)
- Reduced mobility (for details, see Annex 3 Table 5)
- Recent hospitalization (hospitalization within 1 month prior to the index date or at any time during follow-up; see also Annex 3 Table 5)
- History of blood clotting disorders
- Concomitant use of combined hormonal contraceptives
- Concomitant use of hormone replacement therapy

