#### 8.4.2.4.1. Week 0 (Baseline)

Clinical data on demographics, date of diagnosis, IBD phenotype and phenotype history, location of previous IBD surgery, medical history, IBD medication history, and smoking status will be collected. Furthermore, the current clinical disease activity (Harvey-Bradshaw Index [HBI]/Simple Clinical Colitis Activity Index [SCCAI]), biochemical data (Hb, thrombocytes,

leucocytes, alanine aminotransferase [ALT], alkaline phosphatase, C-reactive protein [CRP], creatinine, fecal calprotectin), current IBD medication, and, if applicable, radiologic, and endoscopic information will be collected.

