#### Follow-up

Among women starting filgotinib, the number and proportion who become pregnant during follow-up will be reported. Similarly, the number and proportion of patients who have a new

diagnosis of TB during follow-up, a serious acute infection, a diagnosis of viral hepatitis, concomitant treatment with other immunosuppressants, or who are administered a live attenuated vaccine will be reported. In patients with TB, or a serious infection identified during follow-up, it will be assessed whether treatment was stopped or interrupted after the diagnosis. The proportion of patients who have a test for lipids at around 12 weeks since initiation of filgotinib will be reported.

Should a VTE event occur, subsequent changes to filgotinib use will be reported (filgotinib treatment persistence or discontinuation).

Assessment of the filgotinib maintenance dose during follow-up will also be done in the subgroup of patients at high risk of MACE, VTE, or malignancy. In addition, the average daily dose during the maintenance period and the duration of use during the follow-up period will be reported.

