Long-time smoking (current or past) for > 10 years	no (if not available, might be in medical report)	no (but can be added)	yes (SWIBREG, but suboptimal coverage [approximately 57%])		
Hx of atherosclerotic CVD	no (might be in medical report)	yes (as part of medical history/comorbidity)	yes (NPR)		
Angina	no (might be in medical report)	yes (as part of medical history/comorbidity)	yes (NPR)		
Coronary heart disease	no (might be in medical report)	yes (as part of medical history/comorbidity)	yes (NPR)		
Myocardial infarction	no (might be in medical report)	yes (as part of medical history/comorbidity)	yes (NPR)		
Congestive heart failure	no (might be in medical report)	yes (as part of medical history/comorbidity)	yes (NPR)		
Stroke	no (might be in medical report)	yes (as part of medical history/comorbidity)	yes (NPR)		
Peripheral artery disease	no (might be in medical report)	yes (as part of medical history/comorbidity)	yes (NPR)		

Variable	Availability in individual registries yes/no (additional comments)				
	ENEIDA (ES)	ICC (NL)	SWIBREG (SE)		
Other CV risk factors		yes (as part of medical history/comorbidity)	yes (NPR)		
Diabetes mellitus (type 1 or 2)	yes (if not available, might be in medical report)	yes (as part of medical history/comorbidity)	yes (NPR)		
Hypertension	yes (if not available, might be in medical report)	yes (as part of medical history/comorbidity)	yes (NPR)		
Obesity/BMI	no (might be in medical report)	yes (as part of medical history/comorbidity)	yes (NPR)		
Current malignancy	yes (if not available, might be in medical report)	yes (as part of medical history/comorbidity)	yes (Cancer Register)		
Hx of malignancy	yes (if not available, might be in medical report)	yes (as part of medical history/comorbidity)	yes (Cancer Register)		
SmPC section 4.4: Special warnings and precautions for use: Immunosuppressive medicinal products					
Concomitant use of immunosuppressants/-modulators (e.g. ciclosporin, tacrolimus etc)	yes	yes	yes		
Concomitant use of advanced therapies (e.g. biologics [including TNF $\alpha$ - inhibitors], non-biologics [e.g. S1P receptor agonists)	yes	yes	yes		
Concomitant use of JAKi's other than filgotinib	yes	yes	yes		
SmPC section 4.4: Special warnings and precautions for use: Viral reactivation					
Viral hepatitis	yes	yes	yes (NPR)		

Variable	Availability in individual registries yes/no (additional comments)		
	ENEIDA (ES)	ICC (NL)	SWIBREG (SE)

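### The smoking criterion requires more than 10 years even of current smokers, which the protocol's account of the Article 20 recommendation does not, and no separate current-smoking variable is listed

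*Protocol*

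**What the plan says.** Section 6 describes the groups affected by the restriction in two ways.

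- In its account of the Article 20 outcome, the smoking group is "those who smoke or have done so for a long time in the past".
- In its summary of the updated SmPC Section 4.4, the malignancy paragraph names "patients who are current or past long-time smokers, or with other malignancy risk factors", and the MACE paragraph names "patients who are current or past long-time smokers, and patients with history of atherosclerotic CVD or other CV risk factors". The VTE paragraph brings smoking in indirectly, by restricting use in patients with CV or malignancy risk factors.

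None of these statements gives a number of years.

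The study variable does. Section 8.3.1 lists "Long-time smoking (for >10 years", with a literature citation for the cut-off, and adds that it covers "either current or past smoking". Table 5 repeats the definition in both the box-warning block and the VTE block: "Long-time smoking (current or past) for > 10 years". Neither the baseline list nor Table 5 has a separate item for current smoking.

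On data, Section 8.4.2.4.1 says of ICC at Week 0 that "IBD medication history, and smoking status will be collected". Table 5 nevertheless marks the ICC smoking variable as not available, with a note that it can be added. For SWIBREG it gives coverage of about 57%. For ENEIDA the same variable is marked unavailable in the box-warning block and available in the VTE block.

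Section 8.7 assesses maintenance dose in the "subgroup of patients at high risk of MACE, VTE, or malignancy". The abstract also promises the proportion of patients at high risk.

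**The concern.** The study exists to measure how far prescribers follow the restriction, so membership of the restricted group is its central measurement. If the restriction reaches a current smoker whatever the duration, a patient who has smoked for eight years and has no other risk factor belongs in the group, yet the study variable cannot flag that patient.

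The definitional error runs in one direction. It removes patients from the restricted-use count, so the reported share of filgotinib use in restricted patients comes out too low and adherence looks better. The same patients drop out of the subgroup in which maintenance dose is examined. Adults are eligible from age 18. Young smokers are the least able to exceed 10 years and the least likely to qualify through age 65 or over or through cardiovascular history.

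This is more than a derivation detail for the SAP. Table 5 guides what is abstracted from charts in ENEIDA and what is added in ICC. If the only item collected is a yes/no for more than 10 years, no later analysis can recover current smoking from it.

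**Working it through.** **Step 1: the definitions side by side.**

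| Place | Current smokers | Past smokers |
|---|---|---|
| Section 6, Article 20 outcome | no duration | long time, years not given |
| Section 6, SmPC 4.4 (malignancy, MACE) | ambiguous: long-time may or may not apply | long time, years not given |
| Section 8.3.1 | more than 10 years | more than 10 years |
| Table 5, both blocks | more than 10 years | more than 10 years |

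The study variable fits one reading of the SmPC paraphrase. It does not fit the Article 20 account. The group in dispute is current smokers of 10 years or less.

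**Step 2: the protocol's own precision figure.** Section 8.5 takes an observed high-risk proportion of 10% in 300 patients. SE = √(p(1−p)/n) = √(0.10 × 0.90 / 300) = 1.73%, and 10% ± 1.96 × 1.73% gives 6.6% to 13.4%. Both match the protocol.

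**Step 3: size of the undercount.** Only patients with no other route into the group are lost. Let s be the share of initiators who are current smokers of 10 years or less, and q the share of those with no other criterion (age 65 or over, CVD, another CV risk factor, malignancy). The missed share is m = s × q. The protocol gives neither input, so both are assumptions: s from 2% to 10%, q from 50% to 90%. With a recorded high-risk proportion R = 10%, the captured fraction is R/(R + m).

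| s | q | m (points) | per 300 | per 500 | R + m | captured | m / 1.73% |
|---|---|---|---|---|---|---|---|
| 2% | 50% | 1.0 | 3 | 5 | 11.0% | 91% | 0.6 |
| 5% | 50% | 2.5 | 7.5 | 12.5 | 12.5% | 80% | 1.4 |
| 5% | 90% | 4.5 | 13.5 | 22.5 | 14.5% | 69% | 2.6 |
| 10% | 90% | 9.0 | 27 | 45 | 19.0% | 53% | 5.2 |

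If the recorded group is larger, say R = 30%, the points lost are the same but the relative loss is smaller. The captured fraction is 0.30/0.31 = 97% down to 0.30/0.39 = 77%. The SE is √(0.30 × 0.70 / 300) = 2.65%, so the shift is 0.4 to 3.4 SE.

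At the low end the shift is smaller than one SE. Over most of the assumed range with R = 10% it is larger. Unlike sampling error, it does not shrink as more patients are enrolled.

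**The case against.** The strongest reply is that the study tests adherence to the SmPC and HCP Guide, and that the Table 5 rows sit under SmPC 4.4 headings. In the SmPC paraphrase, long-time can qualify current as well as past smoking, and the variable follows that reading. The cut-off is also deliberate and carries a citation. This stands in part. A reader might infer that the restriction plainly covers anyone who smokes, but the documents do not settle that. The Article 20 sentence separates the two groups, the SmPC paraphrase does not, and the protocol ranks neither above the other. What remains is an unreconciled difference, with no explanation of why the threshold extends to current smokers.

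A reader might also infer that a smoker with no recorded duration counts as a non-smoker throughout. The protocol does not say so. Section 8.7 tabulates missing values and leaves them out of percentages, and Section 8.7.1.3 has SWIBREG describe them. Only ENEIDA (Section 8.7.1.1) treats absent information as absence of the condition, and only in most instances. The nonresponder rule for ICC (Section 8.7.1.2) does not obviously apply to a baseline covariate.

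Third, one could multiply an assumed 10% of current smokers by one third and claim a loss of 3.3 points, or the full 10 points in ICC. Those are gross figures. They ignore entry through other criteria, merge short duration with unrecorded duration, and for ICC assume that duration is never added although Table 5 says it can be. Table 5 gives no reason for the ICC entry, so the duration requirement is only a likely explanation.

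Finally, Section 8.7 does not define the high-risk subgroup, and the SAP may do so. That is fair for the derivation, but not for a variable that the protocol has already fixed.

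**Conclusion.** The concern holds as an internal inconsistency with a one-directional consequence. Section 6 describes the Article 20 recommendation without a duration for current smokers. Section 8.3.1 and both Table 5 rows impose more than 10 years on them and list no separate current-smoking item, although ICC already records smoking status at Week 0.

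Under the Article 20 reading, restricted use is understated and the maintenance-dose subgroup is incomplete. The direction follows from the definitions. The size does not: the range of 1 to 9 percentage points (3 to 27 patients per 300) rests wholly on the assumed s and q, and its upper end needs one initiator in ten to be a current smoker of 10 years or less. Under the other reading of the SmPC paraphrase, requiring a long duration of current smokers is consistent with the text, although the figure of 10 years still does not come from it. Incomplete smoking data in the registries is a separate problem and is not part of this estimate.

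The differing ENEIDA entries for the same variable are an editorial slip. Both point to the medical report as the fallback, so they add no weight.

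**What to change.** - Reconcile the Article 20 and SmPC statements in Section 6 with the variable in Section 8.3.1 and the two Table 5 rows, and state which patients the smoking criterion is meant to identify and why.
- List current smoking at index, of any duration, as a separate variable beside past smoking of more than 10 years. Keep duration for current smokers where it can be obtained. Mark current smoking as available in ICC from the Week 0 smoking status.
- Report the restricted-use proportion and the maintenance-dose subgroup twice: once counting any current smoking, once with the more-than-10-year criterion. Both readings are then visible and neither has to be chosen in advance.
- Show unrecorded duration as its own category in every registry, not as non-smoking.
- Align the two ENEIDA cells for the same variable.

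The cost is wording in Sections 6 and 8.3.1 and Table 5, one item on the ENEIDA abstraction form, and one or two extra table rows. The small downside is a somewhat larger reported restricted-use group under the wider definition. The change concerns what the study measures and does not touch treatment.

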# 7. RESEARCH QUESTION AND OBJECTIVES

Information on prescribing of filgotinib for UC under real-world clinical practice is scarce, specifically, in the context of the updated prescribing information and HCP Guide after implementation of Article 20 decisions on JAKi's.

Therefore, this longitudinal DUS aims to describe physicians' adherence to the prescribing information of filgotinib in real-world clinical practice and to evaluate the effectiveness of the aRMMs by assessing how HCPs prescribing filgotinib adhere to the information provided in the SmPC in conjunction with the information in the HCP Guide with a specific focus on aRMMs implemented after the EC Article 20 decision on JAKi's (i.e. after 10 March 2023).

The objectives of this study are as follows:

- a. To describe the characteristics of patients treated with filgotinib in terms of:
- Demographics (e.g., age and sex)
- Comorbidities and prior and current medication use
- b. To evaluate prescribers' adherence to the filgotinib aRMMs, specifically:
- Compliance with the recommended posology (average daily dose) and duration of use
- Compliance with recommendations for patient screening and laboratory monitoring prior to and during treatment
- Compliance to recommendations for use in patients with moderate to severe chronic renal impairment/end stage renal disease or severe hepatic impairment
- Compliance with recommendations for limitations of use, including:
  - Use in patients with risk factors for venous thromboembolism (VTE)
  - Use in patients aged 65 years and older
  - Use in patients with risk factors for cardiovascular (CV) disease
  - Use in patients with risk factors for malignancy

- Use in patients with risk factors for serious infections
- Use in patients with concomitant use of other potent immunosuppressants
- Use of live attenuated vaccines
- Contraindicated use
- Compliance with discontinuation of filgotinib treatment in patients experiencing VTE

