#### 8.4.2.4.2. Follow-up Visits (Week 12, 24, 52, Year 2, 3, 4, 5, 6, 7, 8, 9, 10)

During follow-up visits, the following information is collected: current clinical disease activity (HBI/SCCAI), biochemical data (Hb, thrombocytes, leucocytes, ALT, alkaline phosphatase, CRP, creatinine, fecal calprotectin), current IBD medication, complications (surgery, hospitalization), AEs (events related to medication and infections), and, if applicable, radiologic and endoscopic information.

Details of variables to be collected in ICC can be found in Annex 3 – Table 5.

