#### 8.7.1.3. SWIBREG (SWE)

Missing baseline values are expected to be rare. For this reason, imputation for missing data points will not be performed in this study. However, variables with missing data will be described.

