Dx date of viral hepatitis	Inconsistently (might be in medical report)	yes	yes (NPR)
Herpes zoster (HZ)	yes (if not available, might be in medical report)	yes	yes (NPR)
Dx date of HZ	Inconsistently (might be in medical report)	yes	yes (NPR)
Screening for TB	yes	no	yes (SmiNet)
Date of screening for TB	yes (possibly in ENEIDA or medical history)	no	yes (SmiNet)
Screening for HZ	yes	no	no
Date of screening for HZ	yes (possibly in ENEIDA or medical history)	no	no
Screening for viral hepatitis	yes	yes	no
Date of screening for viral hepatitis	yes	yes	no
SmPC section 4.4: Special warnings and precautions for use: Haematological abnormalities			
Laboratory measurement of ANC	no (might be in medical report)	no (only total leucocyte count, but it can be added)	yes (currently for <20%)
Date of measurement	no (might be in medical report)	yes (leucocyte count at baseline [week 0])	yes (currently for <20%)
Laboratory measurement of ALC	no (might be in medical report)	no (only total leucocyte count, but it can be added)	yes (currently for <20%)
Date of measurement	no (might be in medical report)		yes (currently for <20%)

Variable	Availability in individual registries yes/no (additional comments)		
	ENEIDA (ES)	ICC (NL)	SWIBREG (SE)
Laboratory measurement of Hb	no (might be in medical report)	yes	yes (currently for <20%)
Date of measurement	no (might be in medical report)	yes	yes (currently for <20%)
SmPC section 4.4: Special warnings and precautions for use: Vaccinations			
Use of live, attenuated vaccines	yes (if not available, might be in medical report)	no (but can be added)	no
Date of vaccine administration	yes		no
HZ vaccination	yes (if not available, might be in medical report)	no (but can be added)	no
Date of vaccine administration	yes		no
SmPC section 4.4: Special warnings and precautions for use: Venous thromboembolism (VTE)			
(Age 65+)	yes	yes	yes
Long-time smoking (current or past) for > 10 years	yes (if not available, might be in medical report)	no (but can be added)	yes (SWIBREG, but suboptimal coverage)
Hx of atherosclerotic CVD	no (might be in medical report)	yes (as part of medical history/comorbidity)	yes (NPR)
Angina	no (might be in medical report)	yes (as part of medical history/comorbidity)	yes (NPR)
Coronary heart disease	no (might be in medical report)	yes (as part of medical history/comorbidity)	yes (NPR)

Variable	Availability in individual registries yes/no (additional comments)		
	ENEIDA (ES)	ICC (NL)	SWIBREG (SE)

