SmPC section 4.4: Special warnings and precautions for use: Infections			

Variable	Availability in individual registries yes/no (additional comments)		
	ENEIDA (ES)	ICC (NL)	SWIBREG (SE)
Acute infection	no (only serious or opportunistic infection can be recorded)	yes	yes (NPR, PDR [prescription of antibiotics])
Dx of acute infection	no	yes	yes (NPR, PDR)
SmPC section 4.4: Special warnings and precautions for use: Viral reactivation	yes (if not available, might be in medical report)		
Viral hepatitis	yes (if not available, might be in medical report)	yes	yes (NPR)
Dx date of viral hepatitis	yes	yes	yes (NPR)
Herpes zoster (HZ)	yes (if not available, might be in medical report)	yes	yes (NPR)
Dx date of HZ	yes	yes	yes (NPR)
SmPC section 4.4: Special warnings and precautions for use: Lipids			
Laboratory measurement of total cholesterol	no (might be in medical report)	no (but will be added)	no
Date of measurement	no (might be in medical report)	(at baseline, week 0), and at follow-up week 12,24, 52 and the year 1, 2, 3)	
Laboratory measurement of HDL	no (might be in medical report)	no (but will be added)	no
Date of measurement	no (might be in medical report)	(at baseline, week 0), and at follow-up week 12,24, 52 and the year 1, 2, 3)	no

Variable	Availability in individual registries yes/no (additional comments)		
	ENEIDA (ES)	ICC (NL)	SWIBREG (SE)
Laboratory measurement of LDL	no (might be in medical report)	no (but will be added)	no
Date of measurement	no (might be in medical report)	(at baseline, week 0), and at follow-up week 12,24, 52 and the year 1, 2, 3)	no
Laboratory measurement of triglycerides	no (might be in medical report)	no (but will be added)	no
Date of measurement	no (might be in medical report)	(at baseline, week 0), and at follow-up week 12,24, 52 and the year 1, 2, 3)	no
Laboratory measurement of HDL:LDL	no (might be in medical report)	no (but will be added)	no
Date of measurement	no (might be in medical report)	(at baseline, week 0), and at follow-up week 12,24, 52 and the year 1, 2, 3)	no
SmPC section 4.4: Special warnings and precautions for use: Haematological abnormalities			
Same as for baseline assessment	no (might be in medical report)	yes	yes (currently for <20%)
SmPC section 4.4: Special warnings and precautions for use: VTE			
VTE event during FU (including PE and deep vein thrombosis)	yes (if not available, might be in medical report)	yes	yes (NPR)
Dx date of VTE	yes	yes	yes (NPR)

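### Table 5 and Section 8.7.1.3 overstate the blood-count data in ICC (no ANC or ALC) and SWIBREG (under 20%), so laboratory-monitoring compliance from them would measure data capture

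*Protocol*

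**What the plan says.** Section 7 of the Protocol sets as an objective "Compliance with recommendations for patient screening and laboratory monitoring prior to and during treatment". Section 8.3.1 names ANC, ALC and Hb under "Laboratory measurements (measurement within ±1 month of filgotinib index date, or any time during follow-up"; Section 8.3.2 lists the same three during follow-up.

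What each registry holds, by Table 5 (Annex 3) and the registry sections:

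- **ICC, baseline.** For ANC and again for ALC: "no (only total leucocyte count, but it can be added". Hb is available with its date. The date cell under ANC is filled with the week 0 leucocyte count; the date cell under ALC is blank.
- **ICC, follow-up.** One row, "Same as for baseline assessment", with an unqualified *yes*. Section 8.4.2.4.2 gives the content of these visits as "biochemical data (Hb, thrombocytes, leucocytes, ALT, alkaline phosphatase, CRP, creatinine, fecal calprotectin".
- **ICC, lipids, for contrast.** "no (but will be added", which is a commitment. ANC and ALC have only a possibility.
- **SWIBREG.** For ANC, ALC and Hb at baseline, and for the follow-up row: "yes (currently for <20" per cent. Long-time smoking is put at roughly 57% coverage. Section 8.7.1.3 says "Missing baseline values are expected to be rare" and gives this as the reason for not imputing.
- **ENEIDA.** ANC, ALC and Hb are not in the registry and might be in the medical report. The footnote to the milestones and Section 8.1 say that chart abstraction is not done for the interim report.

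**The concern.** Two statements cannot stand beside the Protocol's own figures. The ICC follow-up cell is true for Hb but not for ANC or ALC. The SWIBREG missing-data statement is not true of the laboratory variables or of smoking.

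For most variables this would only cost precision. Here the recorded test is itself the outcome. Where the source does not hold the test, a missing entry says nothing about the prescriber, yet it will be counted as something. The study exists to tell regulators how prescribers follow the risk minimisation measures, so a figure driven by data capture could be read as a finding about prescribing. Section 8.9 does not warn of this. It concedes in general terms that registries differ, singles out skin examination as unmeasurable, and describes most SWIBREG variables as available.

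**Working it through.** **1. The Protocol's own precision figure.** Section 8.5 takes p = 10%, n = 300. SE = √(p(1−p)/n) = √(0.10 × 0.90 / 300) = 1.73%, and 10% ± 1.96 × 1.73% gives 6.6% to 13.4%. This agrees with the text. Table 4 also reproduces. The sample-size arithmetic is not in question.

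**2. ICC, side by side.**

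| Variable | Table 5 baseline | Visit content (8.4.2.4.2) | Table 5 follow-up |
|---|---|---|---|
| Hb | yes | listed | yes |
| ANC | no | not listed | yes |
| ALC | no | not listed | yes |

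Only the Hb line is consistent. As now collected, the number of ICC patients with an ANC or ALC value is 0.

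**3. SWIBREG, what would be reported.** Two inputs are needed that the Protocol does not give: whether the figure below 20% is a share of all patients or of tests actually done, and how an absent value is counted. Both are treated as assumptions.

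- *Absent counted as not tested, figure read as a share of patients.* Reported compliance is the figure itself: below 20%, whatever the true testing rate.
- *Absent counted as not tested, figure read as capture c among tests done.* Reported compliance = c × t, with t the true testing rate. For t from 50% to 100%: c = 20% gives 10% to 20%; c = 10% gives 5% to 10%; c = 5% gives 2.5% to 5%. Since c is below 20%, so is the result.
- *Absent excluded from the percentage, as Section 8.7 provides for missing values.* Everyone left in the denominator has a test, so reported compliance is 100% for every t.

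No branch recovers t. The other registries' rules differ again: Section 8.7.1.1 (ENEIDA) mostly reads no information as absence, and Section 8.7.1.2 (ICC) counts missing as non-response.

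**4. Numbers with a value in SWIBREG.** At the cap of 500: fewer than 0.20 × 500 = 100. At 300: fewer than 0.20 × 300 = 60. For a proportion of 10% among patients with a value, SE is at least √(0.09/100) = 3.0%, against 1.3% in Table 4 for 500, and at least √(0.09/60) = 3.9%, against 1.7% for 300.

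**5. Smoking.** (1 − 0.57) × 500 = 215 of 500 without a value at the cap. This bears only on whether missing baseline values are rare; smoking belongs to a different objective.

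**6. Interim.** For ANC and ALC, ICC holds none as now collected, ENEIDA has no chart data, and SWIBREG has fewer than 20%. For Hb, ICC contributes in full.

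**The case against.** The strongest reply is that this is loose wording in a document that already hedges. Variables are collected subject to availability in each registry, Section 8.9 admits uneven capture, Section 8.1 says that the ENEIDA interim lacks charts, and the follow-up row in Table 5 is a composite that could be read as carrying the baseline qualifiers forward. The SWIBREG figure is marked as current, with datasets due in 2027 and 2029. The detailed denominator belongs in the SAP.

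Part of this stands. Capture may improve, and the SAP may choose the denominator. But no denominator rule supplies ANC or ALC values that ICC does not collect, or recovers testing rates from a source that holds fewer than one in five. The conflict between Table 5 and Section 8.7.1.3 also remains.

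Several stronger readings are not supported:

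- *A reader might infer that haematology monitoring can be assessed only from ENEIDA charts and hardly at all at the interim.* That is so for ANC and ALC only. ICC records Hb at baseline (Section 8.4.2.4.1) and at each follow-up visit.
- *A reader might infer that SWIBREG compliance will come out low.* The direction is not fixed; under the Section 8.7 rule it would be near 100%.
- *A reader might state that true testing of 90% would show as 18%.* That is 0.90 × 0.20, which treats the Table 5 figure as capture among those tested. The figure may already be the share of patients with a value.
- *A reader might infer that ICC will analyse total leucocytes as ANC.* One date cell hints at it, but nothing says so, and Sections 8.3.1 and 8.3.2 name ANC and ALC.

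**Conclusion.** The point holds, limited as follows. Table 5 contradicts itself and Section 8.4.2.4.2 on ANC and ALC in ICC. Section 8.7.1.3 contradicts Table 5 on SWIBREG laboratory values (below 20%) and smoking (about 57%). Followed as written, SWIBREG laboratory compliance would be below 20% or about 100% depending on how absent values are counted, and neither figure describes prescribers. ICC can give no ANC or ALC proportion until the fields exist. Hb in ICC is sound at both reports.

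This rests on two assumptions: that the SWIBREG figure stays near its current level, and that it refers to patients or tests in the study population, which Table 5 does not spell out. It should be put right before the interim data are assembled.

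**What to change.** 1. **Table 5, ICC.** Change the follow-up cell to show Hb as available and ANC and ALC as not available until added. Commit to adding ANC and ALC with test dates, in the same firm terms as for lipids, taken from the patient files that Section 8.4.2 says ICC already extracts from. Correct the ANC date cell so that a leucocyte date is not entered as an ANC date.
2. **Section 8.7.1.3.** Replace the statement that missing baseline values are rare with the Table 5 coverage figures for laboratory values and smoking.
3. **Laboratory monitoring.** Report the share of patients with a recorded test as data capture. Do not present it as prescriber compliance from SWIBREG while capture stays at the Table 5 level, nor for ANC and ALC from ICC before the fields are added. Name this gap in Section 8.9.
4. **Interim report.** State that it gives no ANC or ALC compliance estimate unless the ICC fields are in place by then. Hb from ICC can still be reported.

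The cost is two further laboratory variables with dates in ICC, where lipid variables are already to be added, and some protocol wording. The downside is that ANC and ALC compliance will rest on ICC and on ENEIDA charts, with no Swedish contribution unless capture improves.
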